### **7.2.1 Current Treatment Options**

Most patients with localized DLBCL can be cured with conventional combination immunochemotherapy, rituximab, cyclophosphamide, doxorubicin hydrochloride, vincristine sulfate, and prednisone (R-CHOP) or combined-modality therapy, including radiotherapy (Tilly, 2015). Most patients with advanced-stage disease can be cured with a doxorubicin-based combination chemotherapy and rituximab (R-CHOP).

Overall, one third of patients will relapse after first-line treatment (Tilly, 2015). In addition, following the first-line treatment by the standard R-CHOP regimen, less than 10% of patients will experience refractoriness (Coiffier, 2002).

Patients with R/R DLBCL have a poor prognosis due to the lack of effective treatment options.

The standard of care for patients with R/R DLBCL after initial therapy is salvage therapy with platinum-based chemotherapy regimens (ie, rituximab, dexamethasone, cytarabine, and cisplatin [R-DHAP], rituximab, ifosfamide, carboplatin, and etoposide [R-ICE], or rituximab, gemcitabine, dexamethasone, and cisplatin [R-GDP]) if they are deemed to be eligible for high-dose chemotherapy (HDCT), followed by autologous hematopoietic stem cell

transplantation (ASCT) (Tilly, 2015). While approximately 50% to 60% of patients with R/R DLBCL remain sensitive to conventional second-line therapy, only roughly 30% will eventually proceed to ASCT (Gisselbrecht, 2010; Crump, 2014; Van Imhoff, 2017).

After ASCT in first relapse, the 48-month overall survival (OS) is 48% (Gisselbrecht, 2012). Patients who fail the first salvage regimen have a poor prognosis: median OS 4.4 months (Van Den Neste, 2016). In addition, approximately one third of patients consolidated with ASCT in first line will eventually relapse. Despite third-line treatment, the prognostic outlook for those patients is poor as well, with a median OS of 10 months (Van Den Neste, 2017).

In addition, a substantial portion of patients are not eligible for transplantation (Gisselbrecht, 2018), as early as the first relapse, and have a lower survival rate. For those patients, regimens based on the ifosfamide-etoposide combination are generally preferred to the cytarabine-cisplatin combination, with rituximab-bendamustine being a potential treatment option as well (Gisselbrecht, 2018).

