### **7.2.3 Compound Background**

Liso-cel is a genetically modified autologous cell-based product consisting of purified CD8+ and CD4+ T cells, in a defined composition, that have been [REDACTED] transduced ex vivo using a replication-incompetent lentiviral vector expressing a CD19-specific CAR. The CD19-specific CAR consists of an scFv binding domain derived from a murine CD19-specific monoclonal antibody (mAb) (FMC63) and the 4-1BB and CD3 $\zeta$  co-stimulatory/signaling domains. [REDACTED]

In vitro and in vivo studies have demonstrated the ability of liso-cel to proliferate, produce cytokines, and exhibit antitumor activity against CD19-positive cell lines and in tumor-bearing mice. The drug product is provided as CD8+ and CD4+ frozen T cell suspensions, which are thawed and infused [REDACTED]. Administration of liso-cel is preceded by lymphodepleting chemotherapy, most commonly with low-intensity fludarabine and cyclophosphamide to increase the expansion, persistence, and antitumor activity of liso-cel.

The efficacy and safety of liso-cel were demonstrated in Study 017001, conducted under BB-IND 016506, a clinical trial for the treatment of patients with R/R NHL (Abramson, 2020).

Data from Study 017001 in subjects with R/R large B-cell lymphoma, who have failed 2 or more lines of therapy, demonstrate that treatment with liso-cel results in encouraging efficacy outcomes. Among the 256 subjects in the DLBCL Efficacy Set, the overall response rate (ORR) was 73% and the complete response rate (CRR) was 53%. The median duration of response was not reached after a median follow-up of 12 months (95% CI 11.2 to 16.7 months); 60.4% of responders were still in response after 6 months (95% CI: 52.6 to 67.3), and 54.7% after 12 months (95% CI: 46.7 to 62.0). The OS in complete responders has not been reached with a median follow-up of 17.6 months and was 21.1 months (95% CI: 13.3 to NR) for the overall population.

In the safety population, among 269 subjects treated with liso-cel, CRS of any grade was reported in 113 (42%) subjects and 6 (2%) subjects had Grade  $\geq$  3 CRS. Investigator-identified neurotoxicity of any grade was reported in 80 (30%) subjects; 23 (9%) subjects had Grade 3 neurotoxicity and 4 (1%) subjects had Grade 4 neurotoxicity. No Grade 5 CRS or neurotoxicity occurred.

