- **Time to next treatment (TTNT):** TTNT is defined as the time from the date of liso-cel infusion to next treatment of the primary disease (excluding consolidation and maintenance therapies). Patients who did not receive any new treatment for the primary disease before the last contact date or before death will be censored at the last contact date or death date. TTNT will be calculated according to the formula:  
$$\text{TTNT (days)} = \text{date of start of the next therapy line or censoring} - \text{infusion date} + 1$$
- **Time-to-Event (TTE) Analysis:** For DoR, PFS, OS, and TTNT, Kaplan-Meier (KM) estimates and the associated 95% CIs of the median, 25th and 75th percentile will be presented. The 2-sided 95% CIs will be computed using the log-log transformation. The survivor function will be displayed graphically using a KM curve.

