## **9.7.5 Safety Analysis**

### **9.7.5.1 Analysis of the Primary Safety Endpoints**

The primary endpoint is the incidence and severity of the following selected AEs or toxicological symptoms reported post liso-cel infusion.

- Secondary malignancies
- Cytokine release syndrome all grades
- Neurotoxicity all grades
- Prolonged cytopenias
- Pregnancy outcome
- Other AEs considered related to liso-cel treatment (Grade  $\geq 3$ , where applicable):
  - hypogammaglobulinemia
  - tumor lysis syndrome
  - infections
  - organ toxicities
  - other (eg, aggravated GVHD)

The primary endpoints will be analyzed and reported as described in Section 9.7.5.2 (below). Furthermore, suitable measures (incidence proportions and incidence rates) will be calculated with the appropriate time periods and methods. Analyses will be carried out without accounting for competing risks as well as accounting for competing risks using the cumulative incidence function method. Details are described in the SAP.

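### Time to next treatment is censored at death and summarised by Kaplan-Meier alone, so it describes a net quantity with death removed and needs a competing-risk analysis beside it

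*Protocol*

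**What the plan says.** Section 9.7.4.1 of the protocol fixes three things for TTNT:

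- **Event:** the start of the next treatment of the primary disease, not counting consolidation or maintenance. Death is not an event.
- **Patients without the event:** those not re-treated before last contact or death "will be censored at the last contact date or death date". Death is thus handled like the end of observation.
- **Estimator:** "For DoR, PFS, OS, and TTNT, Kaplan-Meier (KM) estimates and the associated 95% CIs of the median, 25th and 75th percentile will be presented", together with a KM curve.

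No competing-risk or composite analysis is stated for TTNT. In the same section, PFS and OS count death from any cause as an event.

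For the primary safety endpoints, section 9.7.5.1 takes a paired approach: "Analyses will be carried out without accounting for competing risks as well as accounting for competing risks using the cumulative incidence function method". Its referral to the SAP for details concerns those endpoints.

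On mortality, section 7.2.1 states "Patients with R/R DLBCL have a poor prognosis due to the lack of effective treatment options". Section 7.2.3 reports that OS in the earlier liso-cel study "was 21.1 months (95% CI: 13.3 to NR) for the overall population".

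**The concern.** A patient who has died cannot start another therapy. Censoring at death treats that patient as if still at risk, with the same future as the survivors. KM then estimates the time to next treatment in a population where nobody dies first, and even that needs death to be independent of the need for treatment.

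Readers of a TTNT curve usually want one of two other things:

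- the proportion who have gone on to further therapy, which 1 − KM overstates;
- the proportion alive and free of further therapy, which the KM curve overstates.

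Deaths before re-treatment cannot be assumed rare in this population, and follow-up runs for up to 15 years. The protocol recognises competing risks in the same cohort for safety but specifies nothing comparable for TTNT. A patient who dies early, without progression or new treatment, is a failure for PFS and a censored non-failure for TTNT, with no reason given.

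**Working it through.** The protocol states no TTNT rate, median or event count, so there is no figure to reproduce. The following is an illustration.

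**Inputs**

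- Hazard of next treatment, a = 0.05/month: assumed, with no source in the protocol.
- Hazard of death without next treatment, d = 0.01, 0.02 or 0.03/month: assumed.
- Only mortality anchor: median OS of 21.1 months (section 7.2.3), or ln 2/21.1 = 0.033/month if constant. This includes deaths after next treatment, so it is an upper-end guide and not an estimate of d.

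**Formulas (constant, independent hazards)**

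- Planned: 1 − KM(t) = 1 − exp(−a·t)
- Actually treated: CIF(t) = a/(a + d) × [1 − exp(−(a + d)·t)]
- Alive and untreated: exp(−(a + d)·t)
- Medians: ln 2/a for the death-censored KM; ln 2/(a + d) for next treatment or death

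**Results at t = 24 months**

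1 − KM = 1 − exp(−1.2) = 69.9% whatever the value of d, so KM shows 30.1% untreated. The KM median is ln 2/0.05 = 13.9 months.

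| d per month | Actually treated | Excess of 1 − KM | Alive and untreated | Median, treatment or death |
|---|---|---|---|---|
| 0.01 | 0.05/0.06 × (1 − exp(−1.44)) = 63.6% | 6.3 points | exp(−1.44) = 23.7% | ln 2/0.06 = 11.6 months |
| 0.02 | 0.05/0.07 × (1 − exp(−1.68)) = 58.1% | 11.8 points | exp(−1.68) = 18.6% | ln 2/0.07 = 9.9 months |
| 0.03 | 0.05/0.08 × (1 − exp(−1.92)) = 53.3% | 16.6 points | exp(−1.92) = 14.7% | ln 2/0.08 = 8.7 months |

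**Sensitivity to the assumed hazards**

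A second grid used net median times to next treatment of 6, 12 or 24 months, and median times to death without treatment of 21.1, 42.2 or 84.4 months (the OS-based hazard, then halved and quartered). Over the nine combinations, 1 − KM exceeded the proportion treated by 1.3 to 10.3 points at 12 months and by 4.1 to 18.5 points at 24 months.

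In the middle case (12 and 42.2 months), 1 − KM at 24 months was 75.0% against 64.7% treated, and the median fell from 12.0 to 9.3 months when death counted. A simulation of 200,000 patients for that case gave 75.1% and 64.9%.

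The direction is the same in every scenario. Only the size depends on the assumptions.

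**The case against.** The strongest defence is that this is a disclosed choice. The event and the rule for death are written down, and KM with deaths censored is a recognised net summary. The protocol nowhere says that the curve is the proportion re-treated or the proportion alive and untreated. Results are descriptive, the primary objective is safety, and PFS and OS show every death alongside. All of this stands, and it limits the harm. It does not supply the missing quantity: PFS uses progression where TTNT uses next treatment, and neither PFS nor OS gives the proportion re-treated.

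The illustration is also soft. Constant hazards fit the protocol's own response data poorly. With ORR 73%, and 60.4% and 54.7% of responders still in response at 6 and 12 months (section 7.2.3), about 0.73 × 0.604 = 44% and 0.73 × 0.547 = 40% of patients were in continuing response, a flattening pattern. A total hazard of 0.07/month gives exp(−0.42) = 66% and exp(−0.84) = 43% alive and untreated, and keeps falling. Response duration is measured from response, so this is a rough comparison, but it is reason not to lean on the exact figures.

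A reader might infer more than the documents support:

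- **That informative censoring has been demonstrated.** The hazards above are independent, so the gaps are differences between estimands. That untreated deaths fall among the sickest patients is plausible, but it is neither stated in the protocol nor modelled here.
- **That KM should be dropped for TTNT.** Section 9.7.5.1 pairs analyses with and without competing risks. Consistency with it argues for adding one and keeping the other.
- **That the cumulative incidence analysis already exists for safety.** It is planned; nothing says that it has been programmed.
- **That the correction makes the product look worse throughout.** The composite median is shorter, but the cumulative incidence shows fewer patients re-treated than 1 − KM.

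**Conclusion.** The point holds as a limitation of what the protocol specifies for TTNT. Event, censoring rule and estimator are all set in section 9.7.4.1, so this is not detail left to the SAP, although nothing prevents the SAP from adding an analysis. As written, the median, quartiles and curve are net of death and can support neither of the two natural readings.

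The direction is certain whenever some patients die before re-treatment. The size cannot be fixed from the protocol: an excess of roughly 6 to 17 percentage points at 24 months rests on assumed constant hazards of 0.05/month for next treatment and 0.01 to 0.03/month for death before it, and the wider grid gives about 4 to 19 points. The primary safety results, the study size and any error rate are unaffected.

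**What to change.** In section 9.7.4.1:

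- Add the cumulative incidence of next treatment, with death without next treatment as a competing event. This is the method that section 9.7.5.1 plans for safety.
- If a median is wanted, add a separately named treatment-free survival, with next treatment or death from any cause as the event, estimated by KM.
- Keep the death-censored KM only under a label that marks it as a cause-specific or sensitivity analysis, and state that deaths are censored.

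No new data are needed: survival status and therapy for relapse or progression are among the variables in Table 3. The cost is a wording change and some extra programming and output. The sponsor should expect a shorter median for treatment-free survival than for the death-censored KM.

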## **9.7.5 Safety Analysis**

### **9.7.5.1 Analysis of the Primary Safety Endpoints**

The primary endpoint is the incidence and severity of the following selected AEs or toxicological symptoms reported post liso-cel infusion.

- Secondary malignancies
- Cytokine release syndrome all grades
- Neurotoxicity all grades
- Prolonged cytopenias
- Pregnancy outcome
- Other AEs considered related to liso-cel treatment (Grade  $\geq 3$ , where applicable):
  - hypogammaglobulinemia
  - tumor lysis syndrome
  - infections
  - organ toxicities
  - other (eg, aggravated GVHD)

The primary endpoints will be analyzed and reported as described in Section 9.7.5.2 (below). Furthermore, suitable measures (incidence proportions and incidence rates) will be calculated with the appropriate time periods and methods. Analyses will be carried out without accounting for competing risks as well as accounting for competing risks using the cumulative incidence function method. Details are described in the SAP.

### **9.7.5.2 General Handling and Analysis of Symptoms or Adverse Events**

The collection of safety data in the registries is specific to certain symptoms of toxicity associated with CAR T cell therapy and recorded as safety outcomes. These include CRS, neurotoxicity, hypogammaglobulinemia, TLS, infections, prolonged cytopenias, organ toxicities and secondary malignancies. All, except for the secondary malignancies, are collected on a calendar format in an aggregate and summarized form based on the prior reporting period. Secondary malignancies, pregnancies and any deaths are reported on an event driven form upon knowledge at the treatment center.

The incidence of organ toxicities will be summarized by Medical Dictionary for Regulatory Activities (MedDRA) System Organ Class (SOC) and Preferred Term (PT). Organ toxicities will be graded using National Cancer Institute Common Terminology Criteria for Adverse Events (NCI CTCAE) version 5.0 or higher. Only organ toxicities of Grade 3 (severe), Grade 4 (life-threatening), and Grade 5 (death) will be summarized in reports. A patient who reports multiple occurrences of organ toxicities with the same SOC and PT is counted only once using the maximum severity grade for summaries. If a patient experiences the same organ toxicity more than once with different grades, then the event with the highest grade will be tabulated in “by grade” tables. If a patient experiences multiple organ toxicities under the same PT and SOC, then the patient will be counted only once for that PT (SOC).

The incidence of each adverse event of interest and of most frequent AEs ( $\geq 10\%$ ) will be summarized using the number and percentage of patients experiencing the event. Exact 95% Clopper Pearson CIs will be provided for the percentages.

Adverse Events will be reported according to the following structure:

- 1) **Overall Summary of Organ Toxicities/Symptoms:** Summaries of AEs will be produced overall as described above.
- 2) **Summaries by System Organ Class and Preferred Term:** Summary tables by SOC and PT of the number of events and the number, percentage, and exact 95% Clopper Pearson CIs for patients having events will be presented separately for each of the event types.
- 3) **Summaries by System Organ Class, Preferred Term, and Highest Grade:** Events will be presented by SOC, PT, and highest grade. Number, percentage, and exact 95% Clopper Pearson CIs of patients for each of the event types will be presented using patient's maximum grade.

Other toxicological symptoms, recorded using free text fields, are coded using SOC and PT based on the most recent version of MedDRA.

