## **9 RESEARCH METHODS**

### **9.1 Study Design**

#### **9.1.1 Study Design**

This study is designed as a noninterventional registry-based cohort study that is based on secondary use of data from existing independent registries of patients with R/R DLBCL, PMBCL, and FL3B after 2 or more lines of systemic therapy, treated with liso-cel therapy in the postmarketing setting, which includes patients treated with OOS product.

Data from at least [REDACTED] patients with a target of [REDACTED] patients – of which a minimum of [REDACTED] patients will come from European countries – will be collected until death or withdrawal of consent or up to 15 years, whichever occurs first.

This PASS is expected to require up to 5 years to select the planned number of patients globally.

This study is a single-cohort study in which all patients are exposed to liso-cel. Hence, its design does not involve any hypothesis testing regarding a potential difference (in safety or effectiveness) between exposed and unexposed patients.

Secondary malignancies must be reported to the MAH by the treating physicians in order to expedite AE reporting. In the event that a secondary malignancy of T cell origin is suspected, the MAH should be contacted to obtain instructions on the collection and transfer of a tumor tissue

sample for testing in a separate process, outside of this PASS. In the postmarketing setting, the MAH will offer transgene assay service testing for all secondary malignancies of suspected T cell origin where a sample is available, as a routine pharmacovigilance measure to ensure gathering the most information possible for clinical assessment of the reported spontaneous case.

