**Table 3: Variables**

Classification	Category	Variable	Description
		Disease Status 2 Disease Stage	Lymphoma staging classification (eg, Ann Arbor Stage I-IV) at diagnosis or infusion
		Disease Status 3 Extranodal Involvement	Extranodal involvement (eg, bone marrow, liver, lung, CNS, and others) at infusion
		Disease Status 4 Lymphoma Classification	Disease subtype (eg, FL3B, PMBCL, DLBCL NOS, HGBCL) at diagnosis
		Disease Status 5 Cytogen. FISH	Double/triple hit (c-MYC, BCL-2, BCL-6 rearrangements) identified via FISH at diagnosis
		Disease Status 6 Cytogen. Karyotyping	Cytogenetic testing via karyotyping at diagnosis
		Disease Status 7 Prognostic Score	Prognostic score (eg, IPI) at diagnosis and/or infusion
		Lymphodepleting Treatment	Types and names of lymphodepleting chemotherapy agents
Outcome (reported at 100 days, 6 months, yearly)	Safety	Secondary Malignancies (SM)	Subsequent neoplasms assessment and types of SM reported during follow-up
		Cytokine Release Syndrome 1 Presence	Assessment and presence of CRS reported during follow-up
		Cytokine Release Syndrome 2 Grade	CRS grade
		Cytokine Release Syndrome 3 Symptoms	CRS symptoms (eg, fever, hypotension, hypoxia)
		Cytokine Release Syndrome 4 Therapy	CRS therapy: intravenous fluids, vasopressors, positive pressure vent support, other therapy (eg, but not limited to tocilizumab), CRS resolution date
		Neurotoxicity (NT) 1 Presence	Assessment and presence of NT reported during follow-up
		Neurotoxicity 2 Grade	NT grade
		Neurotoxicity 3 Symptoms	NT symptoms (eg, aphasia, consciousness, dysphasia, seizure, paraparesis, cerebral edema, hallucination, tremors, other neurologic symptoms)
		Neurotoxicity 4 Therapy	NT therapy: antiepileptic and other therapy given, NT resolution date
		Prolonged Cytopenia 1 Presence	ANC < 500/mm  , platelet count < 20× 10  /L

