### **9.7.2 Analysis of Study Conduct and Study Discontinuation**

An adapted CONSORT diagram will be provided for documenting the number of patients at each reporting schedule. It will also present the patients' situation with regards to their participation in the study and, if relevant, the reason why and when they stopped.

The total number of patients selected from the registries and used within the study, as well as the number and percentage of patients, will also be presented by country and center.

Patient disposition will be summarized and defined as patients who receive liso-cel and are reported to the corresponding registries with either ongoing follow-up, completed follow-up at 15 years or discontinued postinfusion follow-up due to death.

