## 9.7.4 Effectiveness Analysis

### 9.7.4.1 Analysis of the Secondary Effectiveness Endpoints

- **Overall response rate (ORR):** ORR is the proportion of patients with a best overall response of complete response (CR) or partial response (PR), where best overall response is defined as the best disease response recorded from liso-cel infusion until disease relapse or progression or start of new anti-cancer therapy, whichever happens first. If best response is collected by both computerized tomography (CT) and positron emission tomography (PET) methods, best response per PET overrules best response per CT.
- **Complete response rate (CRR):** CRR is the proportion of patients with a best overall response of CR, where best overall response is defined as the best disease response recorded from liso-cel infusion until disease relapse or progression or start of new anti-cancer therapy, whichever happens first. If best response is collected by both CT and PET methods, best response per PET overrules best response per CT.
- **Duration of response (DoR):** DoR is defined as the time from the date of first documented disease response (CR or PR) to the date of first documented progression or first documented relapse, or to date of death due to primary disease, whichever happens first. Patients who are alive and didn't experience disease progression, relapse or death due to primary disease before last contact date will be censored at that time, but no censoring will be done for additional treatment.
- **Progression-free survival (PFS):** PFS is defined as the time from the date of first liso-cel infusion to the date of event defined as the first documented relapse or progression or death due to any cause, whatever happens first. Patients who did not reach such events before the last contact date will be censored at that time, but no censoring will be done for additional treatment.
- **Overall survival (OS):** OS is defined as the time from the date of first infusion to the date of death due to any cause. All patients will be followed for survival information, regardless of whether they receive additional treatment postinfusion. Patients who are alive at last contact date will be censored at that time, but no censoring will be done for additional treatment. OS will be calculated according to the formula:  
$$\text{OS (months)} = (\text{date of death or censoring} - \text{infusion date} + 1) / 30.4375.$$

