## **9.9 Limitations of the Research Methods**

As this is an observational PASS based upon secondary use of data, sporadic missing data are inevitable, because certain variables may not have been routinely recorded in the patient medical charts. Furthermore, data will also be missing due to gaps in the follow-up (as routine scheduled visits cannot be mandated in an observational study), and loss to follow-up, especially in this study

with a planned duration of 15 years. Details of how missing data are handled are also outlined in the SAP.

The above-mentioned potential issue can lead to significant biasing effects on time to event analyses, as well as analyses quantifying a duration. In the EBMT and the CIBMTR registries, data are recorded at baseline, 100 days, 6 months, and then yearly. Thus, owing to center-specific different levels of compliance, a high variability in the recording of assessment dates is to be expected.

To minimize selection bias, treatment centers will be encouraged to include patients in the registries and will be requested to ask every patient treated with liso-cel to share data with the registry. The MAH has implemented a healthcare professionals (HCPs) educational program in Europe that informs HCPs that patients who receive liso-cel are expected to be enrolled in a registry and to be followed in the registry in order to better characterize the long-term safety and effectiveness profile of liso-cel. In addition, the registry holders will provide continuous support and regular training to the treatment centers and will maintain constant contacts with them, emphasizing the importance and purpose of the data collection, and encouraging them to enter baseline patient data promptly and to capture follow-up data continuously. The registry holders will compensate participating treatment centers for data entry into the registries.

Nevertheless, not all patients will consent to have their data sent to the EBMT or the CIBMTR registries, possibly resulting in a biased sample of patients. A high rate of attrition (particularly if mortality is not captured well) could bias the results. In addition, in order to monitor the reporting, the study team will reconcile shipped products to each center participating in the study with the subsequent compliance of the patient and center with the study.

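### Deaths and secondary malignancies arrive on event-driven forms while event-free patients are censored at last contact, which can distort Year 5 survival and malignancy rates; the disposition classes also omit withdrawal and loss to follow-up

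*Protocol*

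**What the plan says.** Two reporting routes are described in Protocol section 9.7.5.2. For the listed safety outcomes: "All, except for the secondary malignancies, are collected on a calendar format in an aggregate and summarized form based on the prior reporting period". For the rest: "Secondary malignancies, pregnancies and any deaths are reported on an event driven form upon knowledge at the treatment center". Section 9.9 gives the routine schedule of both registries: "data are recorded at baseline, 100 days, 6 months, and then yearly".

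The overall survival rule in 9.7.4.1 is: "Patients who are alive at last contact date will be censored at that time, but no censoring will be done for additional treatment". Progression-free survival is censored at last contact in the same way. Section 9.7.5.1 plans incidence proportions, incidence rates and cumulative incidence functions for the primary safety endpoints, the first of which is secondary malignancies.

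Table 3 gives a different account of the reporting route. Its outcome block, which contains both secondary malignancies and survival status, is labelled "Outcome (reported at 100 days, 6 months, yearly". Table 3 also defines last contact by the patient's contact with the site of care and does not say what updates it in the registry.

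On disposition, 9.7.2 describes patients "with either ongoing follow-up, completed follow-up at 15 years or discontinued postinfusion follow-up due to death". Section 9.1.1 says data "will be collected until death or withdrawal of consent or up to 15 years, whichever occurs first", and 9.9 expects loss to follow-up over 15 years.

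**The concern.** Consider a patient whose last yearly form was completed eight months before a data extraction. If that patient dies or develops a second cancer in those eight months, the event-driven form brings the event into the data. If nothing happens, the next yearly form is not yet due and the patient may be censored eight months back. Whether the record is refreshed then depends on the outcome, so the numerator and the risk set cover different periods. Kaplan-Meier estimates fall too fast and person-time rates are too high.

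This matters most when many patients are recent. Selection may take up to 5 years, and an interim report is committed at Year 5 after the European Commission decision. The affected quantities are overall survival, the death component of progression-free survival, and the rate and cumulative incidence of secondary malignancies.

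The disposition sentence adds a second problem. Patients who withdraw consent or are lost have no class, so in that summary they would be counted as ongoing. A reader could not tell current follow-up from overdue follow-up there.

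**Working it through.** The protocol gives no figure for reporting lag, attrition or censoring bias, so there is none of its own to reproduce here. The size below is illustrative.

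**Inputs from the protocol**
- Median overall survival 21.1 months (7.2.3).
- Forms at day 100, month 6, then yearly (9.9).
- Selection over up to 5 years (9.1.1) and a Year 5 interim (Table 2).
- Secondary malignancies 1,950/25,452 = 0.077 (Table 4). No time horizon is given.

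**Assumptions**
- Exponential survival and uniform entry over the 60 months before the cut.
- Events known at once; event-free patients censored at the last due form.
- The 0.077 spread over 5 years, or about 1.5 per 100 patient-years.

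**Person-time by hand**
1. Death hazard: λ = ln 2 / 21.1 = 0.03285 per month, so 60λ = 1.971.
2. True mean follow-up per patient: (1/λ) × [1 − (1 − e^(−1.971))/1.971] = 17.15 months.
3. Time lost between last due form and cut. For a form interval from a to a + w, the integral is e^(−λa) × [1 − e^(−λw)(1 + λw)]/λ². The seven intervals up to month 60 give 5.02 + 3.12 + 12.97 + 37.49 + 25.28 + 17.04 + 11.49 = 112.41. Divided by 60, this is 1.87 months per patient.
4. Share of person-time lost: 1.87/17.15 = 10.9%. Rate inflation: 1/(1 − 0.109) = 1.12.

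**Simulation (400,000 patients, Year 5 cut)**

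| Scenario | Median OS, months | 24-month OS |
|---|---|---|
| True value | 21.1 | 0.455 |
| Censored at last due form | 19.2 | 0.424 |
| Same, forms 3 months late | 18.1 | 0.401 |
| Last contact refreshed quarterly | 20.5 | 0.445 |
| Last contact refreshed monthly | 21.0 | 0.452 |
| Last due form, 10% of deaths never reported | 21.1 | 0.457 |
| Last due form, 20% never reported | 23.5 | 0.494 |
| Last due form, 30% never reported | 26.0 | 0.535 |
| Events and follow-up both cut at last due form | 21.2 | 0.456 |
| Vital status known at the cut-off | 21.2 | 0.456 |

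With a 35% survival plateau, 24-month survival is 0.441 against a true 0.473, an error of 3.2 points.

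The malignancy rate is 1.72 against 1.53 per 100 patient-years, a ratio of 1.12 that agrees with the hand calculation. The ratio is 1.15 with the plateau and 1.20 with forms 3 months late. Cutting events and follow-up alike returns it to 1.53.

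**Later cuts and crude proportions.** At Year 10, without loss to follow-up, there is no survival bias up to 48 months; the malignancy rate ratio is 1.01 (1.05 with the plateau). At Year 15 it is 1.00. A crude malignancy proportion does not use person-time. Leaving out patients with no form yet and no event moves it only from 2.15% to 2.27%.

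**The case against.** The strongest reply is that Table 3 ties last contact to any contact with the site of care, not to a scheduled form. If the registries carry that date up to each extraction, the error shrinks to a point or less. This stands, and it is why the size is conditional. It does not remove the point, because the protocol does not say how the date is refreshed between forms.

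A reader might infer that survival will certainly be understated at every data cut. The documents do not support that. Events are reported only once the center knows of them, and 9.9 warns that mortality may be poorly captured. In the illustration, 10% missed deaths cancel the error at 24 months and 20% reverse it. Table 3 also puts the same outcomes on the calendar schedule; if that is the true route, the asymmetry may largely disappear.

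A reader might also infer that attrition is hidden. That is too strong. Section 9.7.2 also promises an adapted CONSORT diagram with numbers at each reporting schedule and the reason and time of stopping. Section 9.8.2 adds a data quality report before interim and final analyses, and 9.9 a reconciliation against shipped product. What stands is that the disposition definition conflicts with the diagram beside it.

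Finally, a data cut-off rule may sit in the statistical analysis plan, which is not at hand, and 9.7.5.1 and 9.9 defer details to it. Its absence from the protocol is therefore not itself the fault. The reporting routes, the censoring rule and the disposition classes are fixed in the protocol, and those are what need attention.

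**Conclusion.** The point holds in a conditional form. The protocol's text allows events to be counted over a period in which event-free patients contribute no follow-up. If scheduled forms are what mainly refresh last contact, and events are reported promptly and completely, the Year 5 report would understate 24-month overall survival by about 3 points (5.4 with forms 3 months late) and overstate the malignancy rate by roughly 12% to 20%. These figures also rest on uniform 5-year entry and the survival shapes used. The net direction cannot be settled from the protocol. The effect is mainly a Year 5 matter and does not touch the crude percentages with Clopper-Pearson intervals.

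Two inconsistencies stand whatever the size: Table 3 against 9.7.5.2 on how malignancies and deaths are reported, and the three disposition classes against 9.1.1, 9.9 and the CONSORT diagram in the same section.

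**What to change.** - For each report, count events and follow-up to the same point. This can be a common cut-off early enough that scheduled forms covering it have fallen due, or each patient's last completed form. Alternatively, have the registries confirm vital status at the cut-off; for the malignancy rate, malignancy status would need confirming as well. List later events separately.
- Reconcile Table 3 with 9.7.5.2 on the reporting route for secondary malignancies and deaths, and state what updates the last contact date.
- In 9.7.2, add 'withdrew consent' and 'lost to follow-up' as disposition classes, with a rule for when a patient counts as lost. Report follow-up completeness, for example observed over possible person-time to the cut-off.

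The cost is a programming rule, two disposition rows and a wording correction. Truncation leaves the most recent months out of rate and survival estimates, though not out of the listings. Confirming status keeps those months but asks the registries for an extra update before each report.
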